7.4.1.6 Monitoring of Subjects with Adverse Events

AEs are recorded and assessed continuously throughout the trial (see Section 7.4.1.3) and are assessed for final outcome at the End of Trial Visit. All SAEs ongoing at the End of Trial Visit must be monitored and followed up by the Investigator until stabilization or until the outcome is known, unless the subject is documented as “lost to follow-up”. Reasonable attempts to obtain this information must be made and documented. It is also the responsibility of the Investigator to ensure that any necessary additional therapeutic measures and follow-up procedures are performed.

7.4.2 Pregnancy and In Utero Drug Exposure

Only pregnancies considered by the Investigator to be related to trial treatment (for example, resulting from a drug interaction with a contraceptive medication) are considered to be AEs. This study does not allow inclusion of females of child-bearing potential under hormonal contraception. However, all pregnancies with an estimated conception date during the period defined in Section 7.4.1.3 must be recorded by convention in the AE page/section of the eCRF. The same rule applies

to pregnancies in female partners of male subjects. The Investigator must notify the Sponsor/designee in an expedited manner of any pregnancy using the Pregnancy Report Form, which must be transmitted according to the same process as described for SAE reporting in Section 7.4.1.4.

Investigators must actively follow up, document and report on the outcome of all these pregnancies, even if the subjects are withdrawn from the trial.

The Investigator must notify the Sponsor/designee of these outcomes using the Pregnancy Report Form. If an abnormal outcome occurs, the SAE Report Form will be used if the subject sustains an event and the Parent-Child/Fetus Adverse Event Report Form if the child/fetus sustains an event.

Any abnormal outcome must be reported in an expedited manner as described in Section 7.4.1.4, while normal outcomes must be reported within 45 days after delivery.

In the event of a pregnancy in a subject occurring during the course of the trial, the subject must be discontinued from trial medication immediately. The Sponsor/designee must be notified without delay and the subject must be followed as mentioned above.

7.4.3 Clinical Laboratory Assessments

Fasted blood and urine samples will be collected for the clinical laboratory tests (hematology, biochemistry, coagulation, virology, drugs of abuse, hormones, and urinalysis) following the timing noted in the Schedule of Assessments ([Table 1](#)). Additional laboratory safety examinations during the course of the trial are at the discretion of the Investigator.

All blood and urine samples must be clearly identified and will be worked up and analyzed in Nuvisan's clinical laboratory. Any abnormalities in any of the laboratory parameters will be judged by a physician individually in relation to the reference ranges from the laboratory.

The Sponsor should receive a list of laboratory normal ranges before shipment of the IMP. Any change in laboratory normal ranges during the trial should be forwarded to the Sponsor, including laboratory certificates.

All safety laboratory examinations will be carried out under fasting conditions. Some additional parameters may be routinely analyzed by the laboratory after abnormal findings, or requested by the Investigator, including but not limited to eg microscopic differential blood count, direct bilirubin and creatine phosphokinase myocardium/brain type.

In case of positive findings of blood, protein, nitrite or leucocytes in the urinalysis, a subsidiary microscopic examination of the sediment will be performed.

For all findings with major deviation and/or possible pathological relevance, follow-up examinations will be carried out until the deviation returns to normal or the absence of pathological relevance can be confirmed. If a deviation considered clinically relevant has not returned to a

normal or not clinically relevant value when it is checked during the screening laboratory tests, the subject will not be included in the trial. Laboratory abnormalities considered clinically relevant by the Investigator will be reported as AE.

Pregnancy testing (serum or highly sensitive urine, as required by local regulations) will be conducted at Screening, on Day -1 and at the end of relevant systemic exposure of the study intervention to confirm non-pregnant status of female participants as per Inclusion Criteria (Section 5.3.1) the study.

The following parameters will be determined as summarized in [Table 2](#).

The amount of blood sampled in this trial is specified in [Appendix II](#).

Table 2 Clinical Laboratory Evaluations

Biochemistry	Aspartate aminotransferase Alanine aminotransferase Alkaline phosphatase γ-Glutamyl-transferase Lactate dehydrogenase Creatine phosphokinase ^b Amylase Lipase	Bilirubin (total) ^a Cholesterol Triglycerides Uric acid	Sodium Potassium Creatinine Urea Glucose Cystatin C (if applicable)
Hematology	Hematocrit Hemoglobin Red blood cell count Mean corpuscular volume Mean corpuscular hemoglobin Mean corpuscular hemoglobin concentration	Platelet count White blood cell count	White blood cell differentials and absolute counts ^c : Basophils Eosinophils Lymphocytes Monocytes Neutrophils
Coagulation	Prothrombin Time (PT) International Normalized Ratio (INR) Activated partial thromboplastin time (aPTT)		
Urinalysis	pH Nitrite Protein Glucose	Ketone bodies Urobilinogen Bilirubin Urine pregnancy test, females only	Leucocytes Blood Microscopic examination ^d
Urine drug screen	Cocaine Amphetamines Methamphetamines Opiates	Barbiturates Benzodiazepine Methadone Cannabinoids	Tricyclic antidepressants Cotinine Ecstasy
Other tests	Hepatitis B surface antigen Hepatitis C antibody HIV1/HIV2 antibodies Follicle stimulating hormone (if applicable, females only to confirm post-menopausal status) Thyroid stimulating hormone Serum beta-HCG pregnancy test (females only) eGFR ^e Alcohol breath test		

eGFR = estimated glomerular filtration rate, HIV = human immunodeficiency virus, beta-HCG = beta-human chorionic gonadotropin

^a In case of an increased bilirubin (total) the direct bilirubin will be determined.

^b In case of an increased creatine phosphokinase (CK), myocardium/brain type (CK-MB) will be determined; if the ratio of CK/CK-MB is above 6, troponin will be determined as well.

^c In case of abnormal findings, manual differential blood count can be requested by the Investigator.

^d Only if blood, protein, nitrite, or leukocytes are positive on the dipstick.

^e Estimated glomerular filtration rate calculated using the Cockcroft-Gault equation.

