
Table of In-Text Figures

Figure 1	Overall Trial Design	20
Figure 2	Design of the Trial	20

List of Abbreviations

AE	Adverse event
AESI	Adverse events of special interest
ALT	Alanine aminotransferase
ALU	Aluminum
AST	Aspartate aminotransferase
AUC	Area under the plasma concentration-time curve
AUC _{0-∞}	Area under the plasma concentration-time curve from time zero (= dosing time) extrapolated to infinity
AUC _{0-t}	Area under the plasma concentration-time curve from time zero (= dosing time) to the last sampling time (t_{last}) at which the concentration is at or above the lower limit of quantification.
AUC _{extra}	The AUC from time t_{last} extrapolated to infinity
AUC _{extra%}	AUC _{extra} / AUC _{0-∞} in percent
beta-HCG	Beta-human chorionic gonadotropine
BMI	Body mass index
CI	Confidence interval
CK-MB	Creatine phosphokinase - myocardium/brain type
CL/f	Apparent total body clearance considering the fraction of dose (f) absorbed
C _{max}	Maximum plasma concentration
c-Met	Mesenchymal-epithelial transition factor
CRO	Contract research organization
CTCAE	Common Terminology Criteria for AEs
CV	Coefficient of variation
ECG	Electrocardiogram
eCRF	Electronic case report form
eGFR	Estimated glomerular filtration rate
EMA	European Medicines Agency
EudraCT	European Union Clinical Trials Register
FDA	Food and Drug Administration
GCP	Good Clinical Practice
GeoMean	Geometric mean

GMR	Geometric Mean Ratio
h	Hour(s)
HCC	Hepatocellular carcinoma
HGF	Hepatocyte growth factor
HIV1/HIV2	Human immunodeficiency virus 1 and 2
IB	Investigator's Brochure
ICF	Informed Consent Form
ICH	International Council for Harmonisation
IEC	Independent Ethics Committee
IMP	Investigational Medicinal Product
LLOQ	Lower limit of quantification
min	Minute(s)
NCI	National Cancer Institute
NSCLC	Non-small cell lung cancer
PGx	Pharmacogenetics
PK	Pharmacokinetics
QTcF	Corrected QT interval according to Fridericia
SAE	Serious adverse event
SAP	Statistical Analysis Plan
SD	Standard deviation
SUSAR	Suspected unexpected serious adverse reactions
T/R	Test/Reference
$t_{1/2}$	Terminal half-life
TEAE	Treatment emergent adverse event
TF1; TF2; TF3	Tablet Formulation 1; Tablet Formulation 2; Tablet Formulation 3
t_{last}	The last sampling time at which the concentration is at or above the lower limit of quantification
t_{max}	Time to reach the maximum plasma concentration
ULN	Upper limit of normal range

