5.5.2 Withdrawal from the Trial

Subjects must be withdrawn from the trial by the Investigator at any time for any of the following reasons:

- Subject withdrew consent
- Subject lost to Follow-up
- Participation in another clinical study
- Relevant adverse events (AEs), especially SAEs, occur that do not justify the subject's continuation in the study
- Pregnancy
- Protocol noncompliance judged as significant by the Investigator and/or Sponsor
- Use of a non-permitted concomitant drug as defined in Section 6.5.2. However, any medications that are considered necessary for the subject's well-being (eg paracetamol up to 1500 mg per day) may be given at the discretion of the Investigator
- Subject is no longer able to participate for other medical reasons (eg surgery, intercurrent illness)
- Any other condition which to the opinion of the Investigator no longer justifies or permits a safe participation of the subject
- Any of the following individual stopping criteria is met unless deemed unrelated to the IMP by the Investigator with alternate etiology identified:
 - Abnormal clinically relevant vital signs confirmed on 2 or more measurements (minimum 5 min intervals), including abnormal blood pressure
 - hypotension defined as systolic < 80 mmHg and/or diastolic < 40 mmHg, or
 - hypertension defined as systolic > 160 mmHg and/or diastolic > 100 mmHg
 - Abnormal clinically relevant ECG findings, including a corrected QT-interval (ad modus Fridericia; QTcF) > 500 ms or an increase in QTcF > 60 ms compared to baseline, confirmed on ≥ 2 repeat measurements
 - Marked increases in liver or renal parameters (ALT/AST $\geq 3 \times$ ULN, total bilirubin $\geq 2 \times$ ULN, creatinine $> 1.5 \times$ ULN confirmed by ≥ 2 repeat measurements
 - Any clinically relevant symptom or sign which in the opinion of the investigator and/or sponsor warrants subject withdrawal.

If a subject has failed to attend scheduled trial assessments, the Investigator must determine the reasons and the circumstances as completely and accurately as possible.

In case a subject should be withdrawn from the trial, the medical monitor and clinical trial leader at the Sponsor will be informed immediately. If there is a medical reason for the withdrawal, appropriate medical care will be provided.

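### Table 2 footnote b writes the troponin trigger as CK/CK-MB above 6, so, taken literally, troponin is mandatory when the CK-MB share is low and not when it is high

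*Protocol*

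**What the plan says.** Footnote b to Table 2 (Protocol, Section 7.4.3) sets a two-step follow-up of a raised creatine phosphokinase. First: "In case of an increased creatine phosphokinase (CK), myocardium/brain type (CK-MB) will be determined". Second: "if the ratio of CK/CK-MB is above 6, troponin will be determined as well". Both steps are worded as mandatory. The ratio has total CK on top and CK-MB underneath, with no units and no percent sign.

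The List of Abbreviations expands CK-MB as "Creatine phosphokinase - myocardium/brain type". Troponin is named nowhere else in the protocol, so no other text restates, explains or corrects the rule.

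The body of Section 7.4.3 adds general safeguards. On laboratory results as a whole it says "Any abnormalities in any of the laboratory parameters will be judged by a physician individually". For major or possibly pathological deviations it says "follow-up examinations will be carried out until the deviation returns to normal or the absence of pathological relevance can be confirmed". It also says "Additional laboratory safety examinations during the course of the trial are at the discretion of the Investigator".

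**The concern.** The footnote first isolates the myocardium/brain type of CK and then makes troponin the next step. One would expect that step to be taken when the isolated fraction is large. Because CK-MB is in the denominator, the written condition is met when the fraction is small and fails when it is large.

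At stake is a safety rule for healthy volunteers that, followed to the letter, requires the further test in the less suggestive case and does not require it in the more suggestive one. The primary endpoints, the sample size and the error rates do not depend on it.

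**Working it through.** **Inputs.** From footnote b: CK-MB is measured if CK is raised; troponin is measured if CK/CK-MB > 6. From the abbreviation list: CK-MB is the myocardium/brain type. The units are not given; like activity units are assumed unless stated. The CK and CK-MB values below are illustrative, not trial data. The protocol derives no figure on this point, so there is nothing of its own to reproduce.

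**Step 1: turn the ratio into a share.** CK/CK-MB > 6 is the same as CK-MB/CK < 1/6 = 16.7%. At CK = 600 the switch is at CK-MB = 600/6 = 100.

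**Step 2: compare the written rule with two possible corrections at CK = 600.** The first keeps the ratio and replaces above with below. The second reads the 6 as a percentage, CK-MB above 6% of CK, so CK-MB > 0.06 × 600 = 36. Neither can be confirmed from the protocol.

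| CK-MB | Share of CK | CK/CK-MB | Troponin as written | Ratio below 6 | CK-MB above 6% of CK |
|---|---|---|---|---|---|
| 24 | 4% | 600/24 = 25 | mandatory | not mandatory | not mandatory |
| 60 | 10% | 600/60 = 10 | mandatory | not mandatory | mandatory |
| 101 | 16.8% | 600/101 = 5.94 | not mandatory | mandatory | mandatory |
| 150 | 25% | 600/150 = 4 | not mandatory | mandatory | mandatory |

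At 4%, 16.8% and 25% the written rule gives the opposite answer to both corrections. At 10% the corrections disagree with each other, and the written rule agrees with the percentage reading. In like units the written rule therefore fails to require troponin only at shares of 16.7% or more; at low shares it at most over-tests.

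**Step 3: check that the direction does not depend on units.** Let k convert CK-MB to the units of CK, so that the ratio is 600/(k × CK-MB). Doubling CK-MB from 60 to 120 takes the ratio from 20 to 10 with k = 0.5, from 10 to 5 with k = 1, and from 5 to 2.5 with k = 2. A different unit moves the switch point but not the direction.

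**Step 4: bound the occasions.** Table 1 and Appendix II give biochemistry on Day -1, pre-dose, Day 2 and Day 4 of each period, and at the End of Trial Visit. After the first dose that is 2 (Period 1, Days 2 and 4) + 4 (Period 2) + 1 (End of Trial) = 7 samples per subject, or 7 × 18 = 126 at most. This is a ceiling on scheduled samples after dosing, not a count of raised CK values. The protocol gives no rate of raised CK, so the number of subjects affected is unknown.

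**The case against.** **The purpose is inferred.** The protocol never says what the troponin step is for. The algebra is certain; that the direction is wrong rests on the name of CK-MB and on the order of the steps. This stands as a limit on certainty. Nothing in the protocol offers a reason for the opposite direction.

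**It may be loose notation.** The author may have meant CK-MB above 6% of total CK and written the ratio upside down without its unit. That is plausible but cannot be confirmed from the document. It explains how the error may have arisen; the text still instructs the opposite at both ends of the table above.

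**The safeguards cover it.** A reader might infer that the rule bars or drops troponin when CK-MB is high. The documents do not support that. Only the mandatory trigger lapses. CK-MB is still measured, so the high value is seen, and the Section 7.4.3 provisions on physician judgement, follow-up and discretionary tests apply. ECGs are scheduled in both periods (Table 1). Section 5.5.2 has a stopping criterion that begins "Abnormal clinically relevant ECG findings, including a corrected QT-interval" and a catch-all, "Any clinically relevant symptom or sign which in the opinion of the investigator and/or sponsor warrants subject withdrawal". Laboratory values must be normal at Screening apart from minor solitary deviations (Section 5.3.1), and exhausting exercise is barred from 72 h before the first dose (Section 6.5.3). Section 3 reports no clinically significant laboratory or ECG findings in the earlier healthy-subject studies. All of this stands and keeps the consequence small, but it does not make the written trigger correct.

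**Conclusion.** The point holds as one about direction. Taken literally, footnote b makes troponin mandatory at a low CK-MB share and not at a high one, with the switch at 16.7% if both quantities are in the same units. The direction holds in any units; the position of the switch does not. The judgement that the direction is wrong is a reasonable inference, not something the protocol states.

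Two stronger readings are not supported. The documents do not show that the number 6 is wrong, only that the ratio and the inequality together point the wrong way. Nor do they show that subjects would go without cardiac follow-up, given the safeguards above.

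The consequence is minor: one conditional safety footnote in a single-dose study of 18 healthy subjects, with no bearing on the bioequivalence conclusion. It is still an operative instruction and should be corrected.

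**What to change.** First ask the site laboratory which threshold and units were meant, for example whether it was CK-MB above 6% of total CK. Then rewrite footnote b with the ratio inverted, so that troponin is mandatory when CK-MB as a share of total CK exceeds a stated threshold in stated units. Align the matching laboratory instruction.

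Do not simply change above 6 to below 6. If 6% was meant, that edit would remove mandatory troponin at shares between 6% and 16.7% (at CK 600, CK-MB above 36 and up to 100), nearly all of which the present text covers; only a ratio of exactly 6 falls outside both versions.

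The cost is one question to the laboratory, one footnote and one laboratory instruction. No scheduled sample is added.

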7.4.4 Vital Signs, Physical Examinations, and Other Assessments

7.4.4.1 Vital Signs

Blood pressure (systolic blood pressure [mmHg] and diastolic blood pressure [mmHg]) will be measured per the oscillometric method using an automated device, which also indicates the corresponding pulse rate. Blood pressure and pulse rate will be measured after at least 5 min in a supine position, according to the Schedule of Assessments (see [Table 1](#)).

Body temperature will be measured auricular.

Further vital sign measurements during the trial are at the discretion of the Investigator.

7.4.4.2 Physical Examination

A standard examination will be performed including general appearance, skin, head, neck (including thyroid), eyes, ears, nose, throat, abdomen, as well as neurological, peripheral vascular, musculoskeletal, cardiovascular and pulmonary system.

Physical examination will be scheduled according to the Schedule of Assessments (see Table 1). Further physical examinations during the trial are at the discretion of the Investigator. Any relevant findings are to be recorded on the Medical History form in the eCRF (for findings from the past that occurred prior to ICF signature) or on the AE form in the eCRF (for findings presently occurring; events existing but unresolved prior to drug administration).

7.4.4.3 Electrocardiogram

12-lead ECGs will be recorded according to the Schedule of Assessments (see Table 1) using the ECG system Cardio Perfect®, Welch Allyn. The ECGs will be recorded in a supine position after at least 5 min rest.

Per time-point, the ECG will be stored electronically, printed and reviewed in a timely manner by the Investigator. The original printout will be stored with the subject's source data. Electronic data may be transferred to a central ECG laboratory for central reading and further analysis; these results would be reported separately.

ECG printouts will be signed and dated electronically by the person evaluating the ECG. The ECG will be interpreted by the Investigator (normal/abnormal). For abnormal ECGs, the clinical significance (yes/no) must be judged by the Investigator and the abnormality is to be specified.

Additional ECGs during the trial are at the discretion of the Investigator.

7.4.4.4 Alcohol Breath Test

A commercially available breath analyzer (Alcotest 6510, Draeger Safety GmbH) will be used to determine the concentration of alcohol in the subject's breath according to the Schedule of Assessments (see [Table 1](#)).

Additional alcohol breath tests during the trial are at the discretion of the Investigator.

7.5 Pharmacokinetics

7.5.1 Blood Sampling

On the PK profiling day, an indwelling venous catheter will be positioned in a suitable forearm vein for blood sampling and should be kept, if possible, until at least 24 h after dosing. After removing the indwelling venous cannula, samples will be taken by venipuncture.

At visits where assessment time points coincide with each other, the vital signs and ECG assessments should be performed slightly before the specific time point and the PK blood sampling should be performed on time.

Plasma concentrations of tepotinib and its metabolites MSC2571109A and MSC2571107A will be determined in each period according to the sampling schedule outlined in the Schedule of Assessments (see [Table 1](#)). The exact date and time of sample collection must be recorded in the eCRF and will be used in the calculation of PK parameters. Blood samples should be taken as close as possible to the scheduled time points. Samples taken outside of the time periods shown in [Table 3](#) need an explanation and will be considered as protocol violation.

Table 3 Time Windows

Planned Blood Sampling	Time Windows (min)
Pre-dose	- 60
0.25 - 1 h post-dose	± 2
> 1 h - 12 h post-dose	± 5
> 12 h - 48 h post-dose	± 15
> 48 h - 168 h post-dose	± 30

Concentrations of tepotinib and its metabolites MSC2571109A and MSC2571107A will be measured using a validated liquid chromatography-tandem mass spectrometry method at Nuvisan. The assays will be carried out in accordance with the applicable Good Clinical Practice and Good Laboratory Practice regulations and the EMA reflection paper. A separate bioanalytical protocol will be provided before the start of the analytical part of the trial. Full details of the bioanalytical method used will be described in a separate bioanalytical report.

7.5.2

Calculation of Pharmacokinetic Variables

Noncompartmental computation of PK parameters will be performed using the software Phoenix® WinNonlin® 6.4 or higher (Certara, L.P., Princeton, New Jersey). For definitions of PK parameters, see Table 4.

Table 4 Definition of PK Parameters for Tepotinib and its Metabolites After Single Dose Administration

Symbol	Definition
AUC _{0-t}	Area under the plasma concentration-time curve (AUC) from time zero (= dosing time) to the last sampling time (t_{last}) at which the concentration is at or above the lower limit of quantification (LLOQ), calculated per the mixed log linear trapezoidal rule (ie linear up/log down)
AUC _{0-∞}	Area under the plasma concentration-time curve from time zero (= dosing time) extrapolated to infinity, calculated as $AUC_{0-t} + AUC_{extra}$. AUC_{extra} represents the extrapolated part of $AUC_{0-∞}$ calculated by $C_{lastpred}/\lambda_z$, where $C_{lastpred}$ is the predicted plasma concentration at the last sampling time point, calculated from the log-linear regression line for λ_z determination at which the measured plasma concentration is at or above LLOQ
C_{max}	Maximum plasma concentration observed
t_{last}	The last sampling time at which the concentration is at or above the lower limit of quantification
t_{max}	Time to reach the maximum plasma concentration
$t_{1/2}$	Terminal half-life, calculated as $\ln 2/\lambda_z$
λ_z	Terminal rate constant determined from the terminal slope of the log-transformed plasma concentration curve using linear regression on terminal data points of the curve
CL/f	Apparent total body clearance of drug from plasma following oral/extravascular administration, calculated as dose/AUC _{0-∞} , only parent drug, will not be calculated for the metabolites
V_z/f	Apparent volume of distribution during the terminal phase following oral/extravascular administration, will not be calculated for the metabolites
AUC_{extra}	The AUC from time t_{last} extrapolated to infinity
$AUC_{extra\%}$	$AUC_{extra\%} = (AUC_{extra} / AUC_{0-∞}) \times 100$

Individual PK parameters will be calculated using actual sampling times. The pre-dose sample will be considered as if it had been taken simultaneously with the administration of study drug. PK variables will be evaluated and listed for all subjects who provide sufficient concentration-time data.

Concentrations below the lower limit of quantification (< LLOQ), which are before the last quantifiable data point, will be taken as zero for calculating the AUC.

7.6

Biomarkers

Biomarkers are not determined in this trial.

7.7**Pharmacogenetics**

Pharmacogenetic sampling is mandatory for trial participation. An additional separate ICF will be used. One blood sample should be collected in duplicate on Day -1 of the first treatment period prior to administration. The pharmacogenetic samples will be analyzed conditionally in case of unexpected PK profiles. The results of the PGx analysis, as applicable, will be described in a separate report.

Storage and analyses of samples will be handled according to the specifications described in the ICF.

7.8**Other Assessments**

Not applicable.

8**Statistics****8.1****Statistical Hypotheses**

The following null hypothesis for the ratio of the geometric means (GeoMean) will be used to assess bioequivalence

$H_0: \mu_T/\mu_R \leq 0.8000 \text{ or } 1.2500 \leq \mu_T/\mu_R$ for at least one parameter (AUC_{0-t} or $AUC_{0-\infty}$ or C_{max})

$H_1: 0.8000 < \mu_T/\mu_R < 1.2500$ for all parameters (AUC_{0-t} and $AUC_{0-\infty}$ and C_{max})

where μ_T and μ_R are the geometric means for the test and reference treatment respectively.

The test treatment is 5 tablets of the 100 mg dose strength of TF3 and reference treatment is 2 tablets of the 250 mg dose strength of TF3, both under fasting condition.

